2. STUDY OBJECTIVES

2.1. Study Objectives

2.1.1. **Primary Objective**

The primary objective of this study is to evaluate the effectiveness of A-101 45% compared to vehicle when applied to 1 common target wart on the trunk or extremities.

2.1.2. Secondary Objective

The secondary objectives of this study include:

- Evaluate the clinical effect of A-101 45% when applied to all treated warts (Target plus Non-Target Warts)
- Duration of response in all treated warts (Target Warts plus Non-Target Warts)
- Safety of A-101 45%

3. STUDY DESIGN

This is a phase 2, randomized, multi-center, study designed to evaluate the safety and efficacy of A-101 45% compared to Vehicle in subjects with common warts on the trunk or extremities.

During the study, the investigator will identify 1 eligible Target Wart and up to 3 additional Non-Target Warts on each subject on the trunk or extremities. All Target and Non-Target Warts will be treated weekly for 8 weeks.

Subjects will be required to complete a total of 13 study visits. The protocol defined study visits are:

- Visit 1 (Day -13 to 0) screening
- Visit 2 (Day 1) randomization; study medication treatment
- Visit 3 (Day 8) study medication treatment
- Visit 4 (Day 15) study medication treatment
- Visit 5 (Day 22) study medication treatment
- Visit 6 (Day 29) study medication treatment
- Visit 7 (Day 36) study medication treatment
- Visit 8 (Day 43) study medication treatment
- Visit 9 (Day 50) study medication treatment
- Visit 10 (Day 57) follow up evaluations, no Target or Non-Target Wart retreatment
- Visit 11 (Day 78) follow up evaluations, no Target or Non-Target Wart retreatment
- Visit 12 (Day 106) follow up evaluations, no Target or Non-Target Wart retreatment
- Visit 13 (Day 134) follow up evaluations, no Target or Non-Target Wart retreatment; end of study

Refer to Section 4 for a complete list of protocol required study assessments.

A completed evaluable subject is a subject that completes all required treatment Visits (Visits 2-9), completes Visit 13 (end of study visit), has had all Target Warts assessed at these visits and has not had a protocol violation documented during the study.

3.1. Number of Subjects and Study Centers

Approximately 120 evaluable subjects will be randomized to one of two treatment arms at approximately 15 investigational centers in the US.

3.2. Duration of Study

The anticipated time for study enrollment is 3 months. The duration of study participation is anticipated to be a maximum of 155 days per subject. Subjects will have a total of 13 study visits. The maximum anticipated duration for the study is approximately 8 months.

4. STUDY PROCEDURES

The schedule of study activities (including assessments, tests, exams, disease assessments, and study drug administration) beginning with screening and continuing through the end of study are outlined in Table 1. A written, signed informed consent form (ICF)/assent must be obtained from each subject prior to performing any study related procedure (e.g., vital signs, clinical laboratory sampling, urine pregnancy test or photography).

Statistical Analysis Plan for Protocol A-101-WART-202

Aclaris Therapeutics, Inc.

Table 1:Study Procedures

Visit	V1 Sereening	V2	V3	V4	٧5	V6	77	V8	67	V10	V11	V12	V13
Treatment Dav	-13 to 0	-	~	15	22	29	36	43	50	57	78	106	134
Treatment Window	N/A	N/A	±1 day	±4 days	±4 davs	±4 davs	±4 days	±4 davs	±4 davs	+4 davs	±7 davs	±7 davs	+7 davs
Study Procedures													
Informed Consent/Assent	×												
Inclusion	x	×											
Criteria/Exclusion Criteria	V ²												
Medical	< >												
history/demographics	<												
Fitzpatrick Skin Type	X ³												
Vital Signs	X ⁴								×				×
Prior	X ⁵												
Medications/Therapies													
Clinical Chemistry and CBC ⁶	X								Х				×
Urine Pregnancy Test ⁷	×	×							×				X
Target Wart Identification ⁸	Х												
Physician's Wart Assessment ⁹	Х	×	X	X	Х	Х	Х	х	Х	Х	×	×	×
Target Wart Dimensions ¹⁰	×	×	X	×	x	×	×	×	×	×	×	×	×
Standardized Photography ¹¹	Х	×		×					x	x			×
Subject Randomization		X ¹²											
Local Skin Reactions		X ¹³	Х	X	Х	X	Х						
Study Medication Application ¹⁴		×	×	X	×	×	Х	X	x				
Weighing of Study Medication Applicators ¹⁵		x	x	х	Х	х	х	х	х				
Subject Instructions	x	x	×	x	×	×	x	Х	х	х	x	x	

Page 13 of 32 Date: 21 November 2017

202
. 1
WART
01-1
A-1
Protocol
for F
Plan
ysis
Anal
Statistical

										-			
Concomitant therapies ¹⁶		X	Х	Х	Х	Х	Х	X	Х	X	Х	Х	X
Adverse Events ¹⁷		x	Х	×	х	Х	Х	х	Х	Х	Х		
¹ Subject inclusion/exclusion ci	criteria will be re-a	e-assessed	prior to rai	ndomization	during Vi	isit 2.							

¹Investigational sites will assign a unique five-digit subject identifier to each subject at Visit 1. This subject identifier will be used in all study documentation for the duration of the study. Each subject's skin must be assessed during Visit 1 using the Fitzpatrick Skin Type Assessment. Refer to Section Error! Reference source not found. for the

⁴Vital signs [including temperature, pulse, respiratory rate, blood pressure, height and weight (Visit 1 only)] will be measured by a qualified staff member at Visit 1, Visit 9 and Visit 13. ³Prior medications/therapies will be collected for a time-period of 13 days prior to Visit 2. Refer to Section Error! Reference source not found. for a list of permitted and restricted concomitant medications.

⁵A complete blood count (including hematocrit, hemoglobin, platelet count, red blood cell count and morphology, white blood cell count and differential (absolute and %) including basophils, eosinophils, lymphocytes, monocytes and neutrophils and a clinical chemistry panel including albumin, alkaline phosphatase, alanine aminotransferase (ALT), aspartate aminotransferase (AST), blood urea nitrogen (BUN), bicarbonate, calcium, chloride, creatinine, glucose, actate dehydrogenase (LDH), phosphorus, potassium, sodium, total bilirubin, total protein, and uric acid.

⁷ Woman of child bearing potential will be required to have a urine pregnancy test at Visit 1, at Visit 2 prior to randomization, Visit 9 and Visit 13.

⁹The treating investigator will identify 1 Target Wart and up to 3 additional Non-Target Warts on the trunk and extremities.

⁹ The investigator will use the Physician Wart Assessment (PWA) to assess each Target and Non-Target Warts. The investigator must assess the Target and Non-Target Warts prior to application of the study medication at Visit 2-Visit 9. In order to be eligible for randomization at Visit 2, the subject must have a PWA grade ≥ 2.

¹⁰ The investigator will measure the dimensions (longest diameter and thickness) of the Target and Non-Target Warts at Visit 1 and prior to randomization at Visit 2. In order for the subject to be randomized at Visit 2 each Target and Non-Target Wart must have the specific dimensions outlined in Section 5.1. At Visits 3-13 the investigator will measure the diameter of each Target and Non-Target Wart.

¹¹ At Visits 1, Visit 2 (prior to study medication application), Visit 4 prior to study medication application, Visit 9, Visit 10 and at Visit 13, a qualified investigational center staff member will take a photograph of each Target and Non-Target Wart using the Aclaris supplied camera. All photographs will be sent to a central imaging laboratory.

¹² Subjects will be randomized at Visit 2 prior to application of study medication. Investigational study staff will re-confirm subject eligibility prior to randomization.

and subject will assess the Target and Non-Target Warts for LSRs prior to the application of the study medication. The subject will assess LSRs 10 (±4) minutes after the application of A-101 study medication and the investigator will assess for LSRs 20 (± 4) minutes after application of A-101 study medication. Refer to ¹³ The investigator and subject will assess each Target Wart for local skin reactions associated with irritation at Visits 2-13. At Visit 2-Visit 9, the investigator Section 6.1 for the complete list of Local Skin Reaction signs and symptoms.

Page 14 of 32 Date: 21 November 2017

Target Warts will be treated with study medication following randomization at Visit 2. If a Target or Non-Target Wart meets the criteria for re-treatment as wash/submerge the Target or Non-Target Warts for at least 6 hours and they must NOT apply any topical products to the Target or Non-Target Warts for at least ¹⁴The investigator will apply the A-101 study medication to subject 8 to 17 years of age. Subjects 18 years of age and older will apply their A-101 study medication in the presence of the treating physician or a member of the investigational study staff that has been trained on the protocol. All Target and Nondefined in Section Error! Reference source not found. the lesion will be re-treated at Visit 3-9. Following application of study medication, subjects must NOT 6 hours.

¹⁵Sites will be required to weigh all A-101 study medication applicators before and after treatment and document the weight of each applicator in the subject's eCRF.

¹⁶ All concomitant therapies including (topical and oral) prescription medications, over the counter medications and natural supplements and non-drug therapies including chiropractic, physical therapy, and energy based therapy must be documented in the subject CRF. Subjects must not apply any topical products (e.g., moisturizers, sunscreen, etc.) to their Target or Non-Target Warts within 12 hours prior to any study visit.

Error! Reference source not found. for instructions on the reporting of SAEs. Non-serious clinical adverse events will be collected following the application of ¹⁷The reporting period for Serious Adverse Events (SAEs) begins when the subject signs the informed consent and continues through Visit 11. Refer to Section the study medication at Visit 2. Non-serious adverse events that occur between the time of consent and study medication application will be documented as medical history. All safety reporting (AEs and SAEs) will conclude at Visit 11 (approximately 28 days after last study medication application) except for clinical adverse events related to local skin reactions.

Page 15 of 32 Date: 21 November 2017

5. ASSESSMENTS OF CLINICAL EFFICACY

5.1. Target and Non-Target Wart Identification

At Visit 1, the investigator will identify one Target Wart and up to 3 additional Non-Target Warts on the trunk or extremities for each subject for treatment and evaluation.

For this study, the trunk and extremities are defined as:

- The front and back of the torso from the clavicle to the hips, including the buttocks and excluding the genitals and anus
- The arms from the shoulder to the fingertips, excluding periungual and subungual areas
- The legs from the hip to the ankles (including the dorsal side of the foot).

At Visit 1, each Target and Non-Target Wart must:

- Have a longest axis that is ≥ 3 mm and ≤ 8 mm
- Have a thickness ≤ 3 mm
- Be a discrete lesion
- Be, when centered in the circular cutout of the provided template, the only common wart present (Refer to Figure 1)
- Not be periungual, subungual, genital, anal, mosaic, plantar, flat or filiform.
- Not be covered with hair which, in the Investigator's opinion, would interfere with the study medication treatments or the study evaluations
- Not be in an area that may be occluded (*e.g.*, by clothing or footwear or in a skin fold).

Record the location of the Target and Non-Target Wart on the body charts in the CRFs indicating landmarks and distances to assist with confirming the location of the Target and Non-Target Warts at subsequent visits.

At Visit 1, the Investigator and an investigational staff member will identify each Target and Non-Target Wart by placing 2 identification (ID) stickers approximately 180 degrees opposite each other with the identified wart in the center of the area outlined by the provided circular template (diagram not to scale):

Figure 1Target/Non-Target Wart Identification

At Visits 2-13, an investigational staff member (other than the evaluating investigator) will confirm the location of each Target/Non-Target Wart using an appropriate combination of the Visit 1 hard-copy reference prints, Visit 2 photographs and the body charts. The staff member will identify the Target/Non-Target Warts by placing 2 appropriately colored ID stickers, with the Target/Non-Target Wart number written on one sticker, approximately 180 degrees opposite each other with the identified wart in the center of area outlined by the provided circular template.

5.2. Standardized photography

At Visits 1, 2, 4, 9, 10, and 13 a qualified investigational center staff member will take standardized color photographs of each Target and Non-Target Wart.

The photographs are to document the appearance and location of the subjects' Target and Non-Target Warts. The subject's identity will not be revealed in the study photographs.

At Visit 2, the photographs must be taken prior to the study medication application.

Care must be taken to ensure the same lighting, background, subject positioning relative to the camera and camera settings are used for each photograph.

Sites will be provided with photography equipment and supplies necessary for obtaining the Target Lesion photographs. Detailed instructions for obtaining and managing the photographs will be documented in the study specific Photography Manual and provided to the site at the study initiation visit.

5.3. Physician's Wart Assessment (PWA)

The Physician's Wart Assessment (PWA) is the Investigator's assessment of the severity of each Target and Non-Target Wart at a particular time point. The Investigator should NOT refer to any other assessments to assist with this evaluation. This evaluation IS NOT a comparison with the PWA at any other visit.

At every study visit, the Investigator will assess the Target and Non-Target Warts and report the one integer that best describes the Target and Non-Target Wart severity using the following scale. At any visit where a study medication treatment is performed, the PWA must be completed prior to the treatment.

	Physician's Wart Assessment
Grade	Descriptor
0	Clear: No visible wart. No further treatment is indicated
1	Near Clear: A visible wart that is less than 3mm in maximal diameter (or length)
2	A visible wart \geq 3mm and <6 mm in maximal diameter (or length)
3	A visible wart \geq 6mm in maximal diameter (or length)

At Visit 1 for the subject to be enrolled and at Visit 2 for the subject to be randomized each Target and Non-Target Wart must have a PWA grade ≥ 2 .

At Visits 3-9, Target and Non-Target Warts must have a PWA > 0 to be retreated. If the Investigator cannot assess the PWA for a Target or Non-Target Wart (*e.g.*, the Target /Non-Target Wart cannot be visualized because of an LSR such as edema, scabbing, etc.) she/he must report the reason in the subject's CRFs. The Target/Non-Target Wart must not be retreated at that visit, and the subject should be seen at the next scheduled visit.

5.4. Subject Instructions

An investigational center staff member will dispense a Subject Instruction Sheet to each subject at Visit 1 (Refer to Appendix Error! Reference source not found.).

Throughout the study, the subjects should:

- Continue their routine cleansing regimen except they should avoid vigorous scrubbing of the Target/Non-Target Warts (*e.g.*, loofah, back brushes, scrubbing straps, abrasive washcloths, sponges and cleansing pads, etc.)
- Continue their routine cosmetics and skin care products

- Avoid exposing the Target/Non-Target Warts to excessive natural or artificial ultraviolet radiation (*e.g.*, sunlight, tanning beds) and use sunscreen on the Target/Non-Target Warts, if excessive exposure cannot be avoided
- Avoid activities that might irritate the Target/Non-Target Wart
- Avoid the use of self-tanning lotions and spray tans.
- Bring the subject instruction sheet with them to each visit.

On study visit days, the subjects should:

- When appropriate for the Target/Non-Target Wart location wear loose fitting clothing to the visit (Note: clothing that comes in contact with the study medication may be bleached)
- Starting with Visit 2, not apply any topical products to the Target/Non-Target Wart within **12 hours** prior to the visit (Note: routine cleansing products are allowed)
- After the completion of any study visit where a study medication treatment was performed DO NOT:
 - Wash/submerge the Target or Non-Target Warts for at least 6 hours
 - Apply any topical products to the Target or Non-Target Warts for at least 6 hours.

5.5. Other Study Supplies

Aclaris Therapeutics, Inc. will provide:

- An appropriate ruler, or other instrument, for measuring the thickness of all Target/Non-Target Warts dimensions
- Templates for use when identifying Target/Non-Target Warts
- Supplies and instructions for collecting, labeling, shipping and result reporting for the clinical laboratory tests and urine pregnancy tests from a third party
- Equipment, supplies and training for taking standardized photographs
- Scales to weigh all treatment applicators
- Eyewash kits.

6. ASSESSMENT OF SAFETY

In addition to reporting adverse events throughout the study the investigator, a designated and appropriately trained staff member or the subject, will perform the following safety assessments according to the schedules noted below.

The investigational staff member performing the LSR evaluations must not participate in the study medication treatment for the subject being evaluated.

6.1. Local Skin Reactions (LSR)

The LSR assessment is the Investigator's assessment of the signs and the subject's assessment of the symptoms associated with irritation at the Target/Non-Target Wart site (*i.e.*, the Target/Non-Target Wart and the skin immediately surrounding the Target/Non-Target Wart exposed to study medication). The Investigator may refer to previous photographs to assist with these assessments only after the PWA has been performed.

The Local Skin Reaction signs to be assessed are:

- Erythema
- Edema
- Erosion
- Ulceration
- Vesicles/bullae
- Excoriations
- Scabbing.

The Local Skin Reaction symptoms to be assessed (by the Subject) are:

- Stinging/burning
- Pruritus (itch).

At Visits 2-13, the Investigator will evaluate the LSR signs at the Target/Non-Target Wart site(s) as follows:

- At visits where a study medication treatment or retreatment is performed:
 - Perform an LSR assessment prior to any study medication application
 - For treated Target and Non-Target Warts perform an LSR assessment 20 (±4) minutes after the Treatment Completion Time.

At Visits 2-13, the Subject will assess the LSR symptoms at the Target/Non-Target Wart site(s) as follows:

- At visits where a study medication treatment or retreatment is performed:
 - Perform an LSR assessment prior to any study medication application
 - For every treated Target and Non-Target Wart site, 10 (±4) minutes after the Treatment Completion Time, report the average of the severity of the LSR for all symptoms since completion of the study medication treatment.
- At visits where no study medication treatment is performed: • Perform an LSR assessment.

The Investigator and subject should report the one integer that best describes the severity of each LSR sign or LSR symptom for the Target and Non-Target Wart sites using the scale below.

	Local Skin Reactions	
Grade	Descriptor	
0	None	
1	Mild	
2	Moderate	
3	Severe	

6.2. Other Evaluations

At Visit 1, the investigator must determine each subject's Fitzpatrick skin type and document appropriately on the subject's CRF.

Table 2Fitzpatrick Skin Type Scoring System

Skin Type	Description
Classification	
Type I	always burns, never tans (pale white; blond or red
	hair; blue eyes; freckles)
Type II	usually burns, tans minimally (white; fair; blond or
	red hair; blue, green, or hazel eyes)
Type III	sometimes mild burn, tans uniformly (cream white;
	fair with any hair or eye color)
Type IV	burns minimally, always tans well (moderate brown)
Type V	very rarely burns, tans very easily (dark brown)
Type VI	Never burns, never tans (deeply pigmented dark
	brown to darkest brown)

(Fitzpatrick 1988)

Medical history information will be recorded including all medical conditions and disease states that, at Visit 1:

- Are ongoing
- Require concomitant therapy
- Are, in the opinion of the investigator, relevant to the subject's study participation.

7. STATISTICAL CONSIDERATIONS

7.1. Sample Size and Power Consideration

Based on efficacy results from the previous study and the active study medication specified in the current protocol for the same indication, sample size for the current study is anticipated to provide greater than 90% power to achieve statistical significance in the primary efficacy analysis.

7.2. General Statistical Considerations

In general, all listings, summaries and analyses will be done and presented by treatment group. Data listings will be produced for all relevant parameters. Summaries of quantitative variables will include the sample size, mean, median, standard deviation, minimum, and maximum. Ordinal variables will be treated as continuous for analysis purposes. For non-ordinal categorical variables, the summaries will include the number and percent of subjects for each outcome. Unless otherwise indicated, for inferential comparisons, statistical significance will be declared if the two-sided p-value is ≤ 0.05 . No alpha adjustments will be made.

7.3. Analysis Populations and Disposition of Subjects

7.3.1. Analysis Populations

The Safety Population is defined as all subjects who received at least one application of study medication.

The Intent-to-Treat (ITT) population is defined as all subjects who were randomized, received at least one application of study medication and had at least one post-baseline efficacy evaluation. No data imputation will be used for missing data.

The Per-Protocol (PP) population includes all ITT subjects who completed Visit 10 with no major protocol violation and who missed no more than 3 treatment visits. For the Visit 13 analysis, the PP population must also have had a Visit 13.

7.3.2. Subject Disposition

Disposition of subjects will be presented by treatment group for each population. These presentations will include the number of subjects who completed the study and the number who discontinued, as well as the reason for study discontinuation.

7.4. Analyses of Demographics, Baseline Characteristics

Demographic and other baseline variables including age, sex, ethnicity, height, weight, vital signs, and all safety and efficacy parameters related to the subject's condition at Baseline, and including laboratory-based evaluations, will be summarized. Summary statistics (N, mean, SD, median, minimum, maximum, proportions, as appropriate) will be presented by treatment group. Baseline PWA scores will be summarized to show comparability among treatment groups before the start of study medication.

Page 22 of 32 Date: 21 November 2017

7.5. Treatment Compliance

Study medication use and accountability will be presented in a listing. Overall study medication use will be summarized by treatment group.

8. **PRESENTATIONS OF SAFETY INFORMATION**

Descriptive statistics by treatment group will be calculated on the safety parameters collected on or after Visit 3 using the Safety Population, defined as subjects who received at least one application of study medication. Safety summaries will include listings of clinical laboratory values and abnormal values, adverse events incidences within each Medical Dictionary for Regulatory Activities (MedDRA) System Organ Class, and changes from pre-dose values in vital signs. Adverse event summaries will be presented showing the proportion of patients experiencing adverse events, both overall and by MedDRA System Organ Class.

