2.2. Study Rationale

A phase 2 clinical trial was conducted in which subjects were randomized to receive A-101 40%, A-101 45% or Vehicle for the treatment of common warts. Study A-101-WART-201 randomized a total of 98 subjects with a clinical diagnosis of common warts. Subjects received up to 8 weekly treatments with A-101 study medication.

The primary and secondary efficacy endpoints of the mean change from baseline to Visit 10 on the Physician Wart Assessment (PWA) and the proportion of PWA responders at Visit 10, which was defined as target warts judged to be clear or to be clear or mild, demonstrated superiority of A-101 45%, but not 40%, versus vehicle.

Both concentrations of A-101 evaluated were well tolerated. The only TEAEs considered to be treatment-related were application site pain for 2 subjects (all events were considered to be mild and resolved on the same day without intervention) and chlamydial infection for 1 subject. There were no clinically significant changes during the study in laboratory evaluations or vital signs.

A-101 solution 45% demonstrated superiority versus the matching A-101 solution vehicle (and A-101 40%) in physician evaluations of efficacy in treating target warts on the trunk or extremities and was well tolerated with occurrence of local skin reactions that were generally transient. Based on these results a phase 2 study comparing A-101 45% vs Vehicle is warranted.

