¹⁷The reporting period for Serious Adverse Events (SAEs) begins when the subject signs the informed consent and continues through Visit 11. Refer to Section 10.1.2 for instructions on the reporting of SAEs. Non-serious clinical adverse events will be collected following the application of the study medication at Visit 2. Non-serious adverse events that occur between the time of consent and study medication application will be documented as medical history. All safety reporting (AEs and SAEs) will conclude at Visit 11 (approximately 28 days after last study medication application) except for clinical adverse events related to local skin reactions.

Page 23 of 53 Amendment 2 Version 3 Date: 05 December 2017

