10.1.3. Adverse event reporting period

The investigator must start reporting non-serious AEs starting with the subject's first study medication treatment continuing until Visit 11. Non-serious adverse events that occur between the time the subject was consented and the first application of study medication will be reported as medical history.

Reporting for SAEs begins after the subject signs the informed consent and continues until Visit 11 (regardless of relationship to study medication). If a subject experiences a SAE after Visit 11 that is deemed by the investigator to be related to study medication, the investigator must report this to the Sponsor using the study specific SAE report form.

Page 41 of 53 Amendment 2 Version 3 Date: 05 December 2017

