10.2. Reporting Procedures

10.2.1. Procedures for reporting adverse events

At each post enrollment visit, the investigator or designee will question the subject to elicit AEs using a non-directive question such as "Has there been any change in your health since the previous study visit?"

The Investigator/designee will monitor the subject for at least 20 minutes after the Treatment Completion Time at any visit during which a study medication treatment is performed to elicit AEs in a similar manner.

If appropriate, based on the subject's response to non-directed questioning regarding AEs, the investigator or designee will follow-up with directed questions and appropriate evaluations.

Any AE noted during the reporting period must be reported in the source documents and on the appropriate AE CRF.

Page 42 of 53 Amendment 2 Version 3 Date: 05 December 2017 AEs that are defined as "Not Related" to the study medications will be followed until they are resolved or until the subject's last study visit. AEs that are defined as "Related" to the study medications will be followed until they are resolved or, if not resolved after the subject's last study visit, until in the opinion of the investigator, the AE reaches a clinically stable outcome with or without sequelae.

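### Read literally, SAP 8 leaves the Visit 2 post-application skin-reaction scores out of the safety summaries; separately, SAP 9.2 and Protocol 12.3 name different analysis sets for safety from SAP 8

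*SAP*

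**What the plan says.** **Time window.** The opening of SAP 8 reads: "Descriptive statistics by treatment group will be calculated on the safety parameters collected on or after Visit 3 using the Safety Population". Both documents place the first application at Visit 2 (Day 1) and the second at Visit 3 (Day 8).

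SAP 6.1 applies skin-reaction scoring from Visit 2. The investigator scores 7 signs 20 (±4) minutes after treatment. The subject scores 2 symptoms at 10 (±4) minutes, and is asked to "report the average of the severity of the LSR for all symptoms since completion of the study medication treatment". Adverse-event reporting starts on the same day. Protocol 10.1.3 says "The investigator must start reporting non-serious AEs starting with the subject's first study medication treatment continuing until Visit 11", and footnote 17 to Protocol Table 1 says "Non-serious clinical adverse events will be collected following the application of the study medication at Visit 2". Protocol 10.2.1 requires staff to "monitor the subject for at least 20 minutes after the Treatment Completion Time at any visit during which a study medication treatment is performed". Under Protocol 10.1.3, SAEs are reported from consent.

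**Analysis set.** SAP 8 uses the Safety Population, which SAP 7.3.1 defines as everyone with at least one application. SAP 9.2 and Protocol 12.3, in identical wording, compute safety statistics on the ITT population. Their next paragraph says that data from all randomized subjects will be summarized.

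ITT has two definitions. SAP 7.3.1 requires randomization, one application and one post-baseline efficacy evaluation. SAP 9.1 and Protocol 12.2, written for optional efficacy sensitivity analyses, also require completion of Visit 10.

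**The concern.** Safety is a stated secondary objective, and the reactions of interest for a 45% peroxide solution are immediate and local. In the previous trial (Protocol 2.2), the treatment was described as well tolerated with "occurrence of local skin reactions that were generally transient". Of the related application-site pain in 2 subjects, the Protocol says "all events were considered to be mild and resolved on the same day without intervention". A score taken minutes after the first exposure is therefore informative, and a score taken a week later does not replace it.

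The choice of set matters because a subject who stops after the first application, possibly because of a reaction, is treated but has no post-baseline efficacy evaluation. The Safety Population keeps that subject; ITT does not. Two competent programmers working from different sections could produce different skin-reaction tables and different tables of discontinuation due to adverse events.

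**Working it through.** The plan states no figure on this point, so there is none to reproduce. The check sets the passages side by side and counts what is affected.

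**1. What the Visit 3 cut-off removes.** Treatment visits are Visits 2 to 9, which is 8. A cut at Visit 3 keeps 7 of 8 and omits 1/8 = 12.5% of the post-application time points, namely the first exposure.

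- Tables 14.3.5.3 to 14.3.5.6 give the percentage of subjects with Target Wart severity > 0 and > 1. At Visit 2 that is (7 signs + 2 symptoms) × 2 cut-offs = 18 rates per arm, × 2 arms = 36.
- With about 120 subjects, these rest on up to 120 × 9 = 1,080 Target Wart scores.
- These are counts of cells, not estimates of bias.

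**2. Whether another section recovers them.** SAP 7.4 summarizes "all safety and efficacy parameters related to the subject's condition at Baseline". That covers the Visit 2 pre-application score, not the post-application score. Both belong to Visit 2, so a cut by visit number cannot separate them. Visit 3 is Day 8 ± 1, so its pre-application score falls 7 − 1 = 6 to 7 + 1 = 8 days after Visit 2.

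**3. What the cut-off does not touch.** Post-dose vital signs and laboratory tests are scheduled only at Visits 9 and 13. Adverse events that arise between visits and are elicited at Visit 3 are kept.

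**4. The sets compared.**

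| Set | Source | Difference from the Safety Population |
|---|---|---|
| Safety Population | SAP 7.3.1, SAP 8 | none |
| ITT | SAP 7.3.1 | drops treated subjects with no post-baseline efficacy evaluation |
| ITT requiring Visit 10 | SAP 9.1, Protocol 12.2 | if used for safety, drops everyone who left before Visit 10 |
| All randomized | SAP 9.2, Protocol 12.3 | drops no treated subject; can add never-dosed subjects, who are replaced under Protocol 5.5 |

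The Visit 2 wart assessment precedes treatment (Protocol 8.3), so the first scheduled post-baseline efficacy evaluation is at Visit 3.

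**5. Illustration for Table 14.3.1.6 (discontinuation due to adverse events).** Assume 60 treated subjects in an arm, of whom e stop because of an adverse event before any post-baseline efficacy evaluation, with no other such discontinuations. The documents give no value for e.

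| e | Safety Population | ITT (SAP 7.3.1) |
|---|---|---|
| 0 | 0/60 | 0/60 |
| 1 | 1/60 = 1.7% | 0/59 |
| 2 | 2/60 = 3.3% | 0/58 |

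The all-randomized set makes little difference. With 3 events assumed among 60 treated and d never-dosed subjects added, the rate is 3/60 = 5.0% (d = 0), 3/61 = 4.9% (d = 1) and 3/63 = 4.8% (d = 3).

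**6. Which tables are exposed.** SAP 11 lists 7 + 3 + 2 + 12 = 24 tables numbered 14.3. Ten name the Safety Population: 14.3.1, 14.3.1.1 to 14.3.1.5, 14.3.2.1 to 14.3.2.3, and 14.3.5.12. The other 24 − 10 = 14 name no set: 14.3.1.6, 14.3.4.1, 14.3.4.2, and 14.3.5.1 to 14.3.5.11. Of the nine AE and SAE tables (14.3.1.1 to 14.3.1.6 and 14.3.2.1 to 14.3.2.3), eight are labelled. The exposure that remains is mainly the six skin-reaction tables, where both the window and the set are open, and Table 14.3.1.6, where the set is open.

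**The case against.** The strongest reply is that more specific text points the other way. SAP 8.1 summarizes treatment-emergent events and SAP 8.5 summarizes skin reactions by visit, neither with a cut-off. The skin-reaction table titles have none, and Listings 16.2.7.2, 16.2.9.1 and 16.2.9.2 would still show the Visit 2 data. The Visit 3 phrase may simply have meant post-baseline. Seven of the eight post-application time points remain in any case. All of this stands. It makes the omission a risk of the literal reading and limits it to the summary tables; it does not remove the sentence that a programmer would find at the head of the section.

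Three stronger readings are tempting and are not supported:

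- *That adverse-event rates generally depend on which section is followed.* Eight of the nine AE and SAE titles already name the Safety Population. Losing Visit 2 events needs the further assumption that event records are selected by visit, although they are events reported from the first application onward.
- *That safety will be summarized only in Visit 10 completers.* That ITT definition is written for optional efficacy sensitivity analyses. It is the only ITT definition in the Protocol, so the risk is real, but neither document says that it governs safety.
- *That this point settles which ITT definition is right.* The conflict between SAP 7.3.1 and SAP 9.1 is a separate efficacy question, and moving safety to the Safety Population leaves it open.

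The laboratory and vital-sign tables are also unlabelled, but little depends on it. A subject lost before any post-baseline wart assessment has no scheduled post-dose value to lose.

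**Conclusion.** The concern holds in limited form. On a literal reading of SAP 8, the first-exposure post-application skin-reaction scores (1 of 8 treatment visits) drop out of the summaries. Independently, safety is assigned to three sets, and at least one of them can remove a treated subject who left early. The text conflict is certain; its effect is not.

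The effect depends on how the Visit 3 phrase is read, on which set is programmed for the unlabelled tables, and on how many subjects leave before a post-baseline efficacy evaluation. The documents give neither that number nor its split by arm, and the illustration shows no difference when it is zero. The previous trial reported related site pain in 2 of 98 randomized subjects across all its arms, so absolute effects may be small. Safety is descriptive only, the primary analysis is unaffected, and nothing is hidden from the listings. The point is worth fixing before programming because the correction costs almost nothing.

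**What to change.** **(a) SAP 8.** Replace the limit to data from Visit 3 onward with: *collected after the first application at Visit 2 onward, including the Visit 2 post-application skin-reaction scores*. State also that SAEs are reported from consent and that pre-dose SAEs are listed, so that the new start point does not cut them out.

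**(b) SAP 9.2 and Protocol 12.3.** Replace the ITT population with the Safety Population as defined in SAP 7.3.1. Replace the sentence on all randomized subjects with: *Safety data will be summarized for the Safety Population; subjects randomized but never dosed will be listed*.

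**(c) SAP 11.** Name the Safety Population in the 14 unlabelled Section 14.3 titles. The SAP already allows titles and footnotes to be modified.

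**Route and cost.** Wording changes in three sections plus clerical titles; no new data and no change to any efficacy analysis. The SAP is dated 21 November 2017 and the Protocol version 5 December 2017, so the existing SAP cannot simply be said to supersede the later Protocol. Use either a protocol amendment under Protocol 13.1 or a SAP revision dated after 5 December 2017 that records the departure from Protocol 12.3. The two ITT definitions should be handled separately as an efficacy matter.
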